III. Preliminary Studies/Progress Report:

Introduction: The preliminary data presented below provide support for the proposed hypotheses and demonstrate my ability to perform the proposed studies with the mentorship and training described in the career development plan. The data fall into three main categories: (1) data collected in a sub-study of the NIH-CACTI study (PI [name]) measuring insulin action in a subset of T1D and non-DM subjects from the CACTI cohort in which I was extensively involved, (2) analyses of data from the overall CACTI study generated specifically in response to this sub-study, and (3) data from [name] demonstrating our ability to measure insulin signaling in tissue biopsy samples.

CACTI study: We are prospectively following CAC in a large cohort of T1D and non-DM subjects. The study enrolled 1,416 individuals between 19 and 56 years of age with no known history of CVD. Subjects with T1D (n=652) had longstanding T1D, were insulin-dependent within a year of diagnosis, and were either diagnosed at <30 years of age, antibody positive, or had a clinical course consistent with T1D. Visits for measurement of CAC by electron beam CT occurred at baseline, year 3, and year 6. The overall CACTI study has been described elsewhere^{44, 45}.

IR sub-study: 87 subjects (40 T1D, 47 non-DM) were recruited from the CACTI cohort to undergo 3-stage hyperinsulinemic euglycemic clamps for measurement of insulin action. Subjects were excluded for HbA1c >9.5 or macroalbuminuria. Baseline characteristics are shown in Table 1. T1D and non-DM groups were well matched for age, BMI, body fat, and habitual physical activity. T1D subjects had higher HbA1c and fasting glucose values as expected. In addition, significant differences were found in LDL, total cholesterol, triglycerides, and adiponectin, with T1D subjects having “better” (i.e. lower CVD risk) values in all categories. Though liver fat has been found to be a strong indicator of IR in T2D, we observed no differences in a measure of liver fat content, liver:spleen density ratio. *These data show that the T1D subjects in our sub-study cohort do not exhibit a metabolic phenotype by criteria of HDL, TG, waist circumference, blood pressure, or BMI. In fact, by lipid criteria, our non-DM cohort appears more IR than our T1D cohort.*

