LDL-cholesterol	67.6 ± 24.8	96.1 ± 26.0	<0.0001
Systolic blood pressure (mmHg)	114 ± 11	113 ± 10	0.61
Diastolic blood pressure (mmHg)	73 ± 7	76 ± 8	0.09
On Htn meds (%)	45	13	0.0005
Habitual physical activity (logkcal)	7.2 ± 1.2	7.4 ± 7.1	0.42
Adiponectin (geometric mean±SD)	10.9 ± 1.7	8.2 ± 1.8	0.02
Cortisol	11.8 ± 4.3	11.5 ± 4.4	0.8

Table 3: Glycemic control and IR			
		correlation to GIR	
		Mean ± SD	r-value
HbA1c		7.5 ± 0.9	0.13
CGM parameters:			
Mean glucose		141 ± 26	0.2
% > 180		26.2 ± 12.9	0.25
% < 70		16.2 ± 11.9	-0.02
Overall SD		65.9 ± 20.1	0.21
			0.22

Adipocyte IR in T1D: Early clamp stages with lower insulin infusion rates reveal the novel finding that adipocyte IR is also greater in T1D than in non-DM subjects (Fig 2). Baseline fasting NEFA levels did not differ by diabetes status, and, as expected, were higher in women (620±26) than in men (463±32), $p=0.0004$. At 8mU/m²/min of insulin (clamp stage 2), NEFA levels were more suppressed in non-DM (193±24 μ M) than T1D (370±26) subjects, $p<0.0001$. In addition, the sex difference observed at baseline is reversed in non-DM, but not T1D subjects, such that the highest NEFA levels are in T1D women (405±33), while the lowest levels are in non-DM women (137±29), $p<0.0001$, indicating greater relative adipose tissue IR in T1D women than men. The observation that fasting NEFA levels are not different by diabetes status despite overnight IV insulin to normalize AM glucose levels and resulting high AM insulin levels in T1D subjects also supports adipose tissue IR in T1D. Glycerol levels show a similar pattern (not shown), suggesting that failure of NEFA suppression reflects failure to suppress lipolysis, a potential mechanism for a role of IR in CVD.

Coronary artery calcification in T1D: 6 year

CAC data for the entire T1D cohort were examined in linear regression models. Adjustment for standard CVD risk factors attenuated the increased risk of CAC progression, but did not eliminate it. In a forward selection multivariate analysis after adjustment for all standard cardiac risk factors that affect the model, including presence of CAC at baseline, the OR of progression of CAC from baseline to 6 years in T1D relative to non-DM was maximally decreased by 49.7% to 1.7 (1.1-2.6). Thus only half of the increase in 6 year progression of CAC in T1D is explained by known CVD risk factors.

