Correlation of CAC to IR: Presence of CAC and progression of CAC were found to correlate inversely with GIR and directly with NEFA levels during clamp stage 2 for both T1D and non-DM groups after adjustment for age (Table 4)⁴⁷. By logistic regression analysis the odds ratio for existence of CAC is 0.45 for every 1 SD increase in GIR and 2.4 for every 1 SD increase in stage 2 NEFA levels. These data support the underlying rationale for studying IR in T1D, indicating that as in other populations, IR is a correlate and predictor of CVD.

Increased vascular stiffness in T1D correlates with an estimate of IR:

Measurement of pulse wave augmentation index (AI), a measure of arterial stiffness, has been performed in a large subset of the CACTI population (n=385). After adjustment for age and gender, AI remains significantly greater in T1D than non-DM subjects (mean, 95% confidence interval: 19.5, 18.2 - 20.7 vs. 16.6, 15.4 - 17.7; $p=0.0011$). When estimated glucose disposal calculated by the Pittsburgh prediction equation³⁰ is added to the model the effect of T1D is completely lost, suggesting that the increased arterial stiffness seen in T1D may be explained by their increased IR.

[figure not shown]

Figure 2 §Least square means adjusted for age, BMI (kg/m²), gender, starting glucose concentration, and time point insulin level. * $p < 0.05$ for difference by diabetes in men; # by diabetes in women; † $p < 0.05$ for sex difference in DM; ‡ in nonDM.

	Spearman correlation coefficient IR vs CAC volume for total cohort (n=87)		
	V3 CAC volume	Baseline to V3 change in CAC	V2 to V3 change in CAC
GIR (mg/kg FFM/min)	-0.42 ($p<0.0001$)	-0.41 ($p<0.0001$)	-0.24 ($p=0.028$)
Stage 2 NEFA level (μ M)	0.41 ($p<0.0001$)	0.40 ($p=0.0001$)	0.27 ($p=0.01$)
		Logistic regression analysis Odds ratio for any CAC at visit 3 (n=87)	
		OR per 1 SD change	p-value
GIR (mg/kg FFM/min)	0.45 (0.22-0.93)	0.03	
Stage 2 NEFA level(μ M)	2.40 (1.08-5.32)	0.032	

Table 4 : IR predicts CAC and correlates with CAC volume

IV. Research Methods

A. Outcome Measure(s):

- Primary outcomes (post each intervention period (placebo vs Metformin): (1) Glucose infusion rate (GIR) during high insulin infusion in hyperinsulinemic euglycemic clamps, (2) Endothelial function measured as percent flow-mediated brachial artery dilation (FMD),

- Secondary (confirmatory and exploratory) outcomes (post each intervention period (placebo vs metformin):
 - NEFA suppression during clamp stage 2,

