 - arterial stiffness (PWV and AI),
 - CGM measures of hyperglycemia, hypoglycemia, and glycemic variability for one week prior to each clamp,
 - Metabolic (NEFA, lipids, insulin, glucose), inflammatory (IL-6, TNF- α , hsCRP, adiponectin), thrombotic (PAI-1), oxidative stress (urinary isoprostanate, TBARs), and endothelial (ICAM, endothelin-1) markers at baseline each study day,
 - Counter-regulatory hormones (cortisol, growth hormone, glucagon, and catecholamines prior to each clamp,
 - Respiratory quotient at baseline and after low dose insulin infusion,
 - Heart rate variability,
 - Mitochondrial content (DNA and electron transport chain complexes),
 - Mitochondrial function (carbohydrate and lipid oxidation, max state 3 O₂ consumption, uncoupled O₂ consumption),
 - Mitochondrial state 3 O₂ consumption,
 - Mitochondrial oxidant generation (H₂O₂ production, glutathione redox state), and
 - Mitochondrial ATP production/ADP depletion by 31P-MRS.

[figure not shown]
B. Description of Population to be Enrolled: Study Design and Research Methods

Hypotheses: Metformin will improve (1) insulin action, (2) vascular function and compliance, and (3) mitochondrial function and oxidant generation in T1D subjects supporting a therapeutic role for metformin in T1D management, including CVD risk management.

Specific Aims: **Specific Aim 1:** Determine the effect of metformin on IR in T1D. **Specific Aim 2:** Determine the effect of metformin on vascular correlates of IR. **Specific Aim 3:** Determine the effect of metformin on mitochondrial function and oxidant generation.

Overall research plan: I propose to address these hypotheses and aims with a single-blinded, fixed-order, placebo-controlled cross-over design study in T1D subjects. The intervention will consist of 6 weeks of treatment with metformin, separated from the placebo period by a \geq 2 weeks washout period. The fixed order is needed because we and others have found persistent residual effects from metformin treatment, and the necessary washout period is not known. Metformin has been studied to a limited degree in T1D, primarily in terms of glycemic control. It has been found to be safe and well-tolerated in these studies (Vella) and the proposed dose and duration have precedent in the literature. [name] at this institution has performed a study using metformin in T1D youth. From his contact with the FDA, an IND is not required for this study.

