Stage 2 (Study drug B, Metformin):

- Visit 6: Stage 2 start visit (Day B1) - Insert CGM and receive instruction on use and download, pick up Metformin, Instructions from PI re med dosing and insulin dose self-adjustment
- Option for one week visit 6b if desired for first repeat CGM insertion
- Visit 7: Stage 2 prestudy visit (Day B39) - pick up three day diet and receive instructions on insulin dosing and times for the pre-study day. Accelerometer set-up
- Visit 8: Admission for Metformin study day (Days B42,43) - see below

During the study visits procedures will include the following: baseline blood draws for inflammatory, metabolic, endothelial, and thrombotic markers; heart rate variability; vascular function and stiffness by flow-mediated dilation (FMD), plethysmography, brachial artery distensibility, and pulse wave velocity (PWV), and augmentation index (AI); insulin sensitivity by 2-stage hyperinsulinemic clamp (8, 40 mU/m²/min) with glucose tracer; muscle biopsies preclamp. If blood sugar at start of the tracer infusion and of the clamp is <60 or >180, the study visit will be concluded without the clamp.

³¹P-MRS optional substudy: DRI pilot funding has been obtained to add a ³¹P-MRS study (method described further below) to the late afternoon preceding each admission to the CTRC for 10 of the MeT1 subjects. On recruitment into MeT1, subjects will be given the option to enroll in this additional sub-study. Specific exclusion criteria for this sub-study will include presence of any metal or other contraindications to MRS, including significant claustrophobia. A separate opt-in section in the consent form will be prepared and submitted to the IRB for this sub-study. Once 10 subjects have opted in and completed, the sub-study will be considered complete and closed to further enrollment. At that point, an interim analysis, including unblinding of these 10 subjects, will be performed. Those who opt in to the sub-study will follow the original study design exactly, with the exception that on day 3 of their study diet, they will be asked to present to the UCD Brain Imaging Center (behind the Leprino Building) in the late afternoon (fasting since lunch; 4-6 hours) for the MRS scan and then proceed to the CTRC for admission for the full study day the following day.

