Hyperinsulinemic euglycemic clamp with tracer infusion: In order to determine insulin sensitivity, subjects will be admitted to the CTRC and fasted for ≥ 12 hr for a hyperinsulinemic euglycemic clamp by the method of deFronzo et al⁶³ omitting the lowest insulin stage (4mU/m²/min) with 6.6 ²H-glucose infusion (4 minute prime at 3mg/kg/min, then 0.04 mg/kg/min) for 2 hours preceding the clamp to allow differentiation of hepatic and muscle insulin sensitivity. Two intravenous cannulae will be established: one for infusions, and the second in retrograde fashion in a dorsal vein of the opposite arm for blood sampling. To obtain arterialized venous blood samples, this hand will be kept warm with a heating pad. Tracers will be initiated at T=0 (about 7AM) and continue for 2 hours. Blood samples will be drawn at T=100, 110, and 120 for tracer and metabolite analysis. A descending primed continuous infusion of insulin (final 8 mU/m²/min) will be initiated at T=120 and continued until T=240 min, then increased with a second descending prime to 40 mU/m²/min for an additional 120 minutes for determination of insulin sensitivity. Plasma glucose will be maintained at 90 mg/dl by variable infusion of 20% dextrose (spiked with tracer). An infusion of potassium will also be given to maintain normal potassium concentration. The rate of glucose infusion will be adjusted based on arterialized blood specimens drawn every 5 minutes, with plasma glucose quantified using a TMAnalox glucose analyzer at the bedside. Blood samples will also be obtained for determinations of free fatty acids, triglycerides, insulin, and glycerol at 60 min. intervals and three times over the last half hour of each stage (as above). After insulin infusion is stopped, glucose infusion will be continued until the subject has completed a standard meal, and plasma glucose levels measured every 15-30 min. for an hour to check for possible hypoglycemia. The subject will then be discharged.

Blood collection and preparation: During the screening visit 1, non-fasting blood and urine sampling (chemistry-7, complete blood count, HbA1c, liver function tests, TSH, pregnancy test, and urine

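### Does the NEFA secondary outcome at clamp stage 2 leave open which insulin step is analysed?

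*Combined protocol and SAP*

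**What the plan says.** The secondary outcomes in section IV.A include "NEFA suppression during clamp stage 2", with no insulin rate or sampling times. Two other clamp outcomes in the same section are identified by insulin level instead: the primary outcome "Glucose infusion rate (GIR) during high insulin infusion in hyperinsulinemic euglycemic clamps" and the secondary outcome "Respiratory quotient at baseline and after low dose insulin infusion".

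The stage number appears earlier, in section III. There the sub-study participants were recruited to "undergo 3-stage hyperinsulinemic euglycemic clamps for measurement of insulin action", and the paragraph on adipocyte insulin resistance reports "At 8mU/m²/min of insulin (clamp stage 2), NEFA levels were more suppressed in non-DM".

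The present trial uses a shorter clamp. The study-day procedures give "insulin sensitivity by 2-stage hyperinsulinemic clamp (8, 40 mU/m²/min) with glucose tracer". The clamp method in section D describes "omitting the lowest insulin stage (4mU/m²/min" and a first step at 8 mU/m²/min, "then increased with a second descending prime to 40 mU/m²/min for an additional 120 minutes". Free fatty acids are drawn hourly, with three further draws near the end of both steps. The Statistical Analysis Plan in section F says only that secondary measures are compared in the same way as the main ones. It gives no stage or rate for NEFA.

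**The concern.** A reader who goes from the outcome list straight to the clamp method finds two steps and may count to the second, which is the 40 mU/m²/min step. A reader who has the preliminary data in mind takes the same words to mean 8 mU/m²/min. Because NEFA is sampled in both steps, either choice gives a complete dataset, and a mistaken choice would not show up as missing values.

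Two things would be at stake. First, the stage-specific NEFA evidence in section III was obtained at 8 mU/m²/min: the contrast between type 1 diabetes and non-diabetic participants, and the Table 4 associations with coronary calcification. A result at 40 mU/m²/min would not follow on from that evidence. Second, if the label really allowed either step, the choice could be made after results were seen. Only the participant is described as blinded to the fixed treatment order, and no multiplicity correction applies to secondary outcomes.

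**Working it through.** No sample size, power or alpha figure depends on this point, so the check is a comparison of passages with some clock arithmetic.

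**Step 1. Timing of this trial's clamp (section D).** The 8 mU/m²/min step runs from T=120 to T=240 min. The 40 mU/m²/min step lasts a further 120 min, so it ends at 240 + 120 = 360 min. The closing half hours are 240 − 30 = 210 to 240 min and 360 − 30 = 330 to 360 min. The ratio of insulin rates is 40/8 = 5. The two readings therefore give distinct quantities.

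**Step 2. Every place that bears on the stage number.**

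| Place | What it shows | Favours |
|---|---|---|
| III, IR sub-study; Table 2 | Earlier clamp had three stages; Table 2 reports stage 3 | Stage 2 was a middle step |
| III, Adipocyte IR in T1D | Clamp stage 2 defined as 8 mU/m²/min; finding attributed to the early, lower-rate stages | 8 |
| III, Correlation of CAC to IR; Table 4 | Same stage label for NEFA, immediately before section IV.A | 8 |
| I, SA#1; study-day procedures | Two steps, 8 and 40, not numbered | Neither by name; 40 by literal count |
| D, clamp method | Lowest stage (4 mU/m²/min) omitted; steps not numbered | 8, if the old numbering is kept |
| IV.A, primary outcome | The 40 step is identified as high insulin | 8, weakly: the list already has a name for the 40 step |
| F, Statistical Analysis Plan | No stage or rate for NEFA | Neither |

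**Step 3. Reading the table.** There is one explicit definition, 8 mU/m²/min, and no competing one. The 40 mU/m²/min reading comes only from counting unnumbered steps and setting the definition aside. It would also move the outcome away from the low insulin rates at which section III reports the adipose tissue difference. Stage 2 is also the name of the metformin treatment period in the visit schedule, but the word clamp in the outcome line rules that meaning out.

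**Step 4. Effect on results.** The document gives NEFA at 8 mU/m²/min (193 μM in non-diabetic and 370 μM in type 1 diabetes participants). It gives no NEFA values at 40 mU/m²/min and no within-person effect of metformin on NEFA. The consequence of choosing the wrong step therefore cannot be sized from the document. Under the defined reading, nothing in the planned analysis changes.

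**The case for a change.** The strongest argument for a change is that the plan never says the earlier numbering is kept. The protocol calls this clamp two-stage more than once. The omitted 4 mU/m²/min stage is tied to a cited clamp method rather than expressly to the sub-study, and the insulin rates of the sub-study's first and third stages are not stated. That the label was carried over is thus an inference. A programmer given only the outcome list and the clamp method could choose 40 mU/m²/min. NEFA may also attract interpretation, since section G discusses NEFA lowering as a possible therapeutic target. Naming the rate would cost one line.

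What stands is that the label is untidy and that a literal count gives the other step. What does not stand is the claim that the plan leaves the choice free. Selecting the step after seeing results would mean disregarding the only definition in the document, and any reader could point that out. It also goes too far to say that all the NEFA rationale lies at 8 mU/m²/min. Section III argues from fasting NEFA as well, and section IV cites lipid-infusion data on arterial stiffness. Neither of these supports a 40 mU/m²/min outcome.

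Naming the rate would not fully fix the outcome either. Whether suppression means the level reached or the change from baseline would still be unstated. That is ordinary analytic detail for an outcome of this rank.

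**Conclusion.** No change to the plan follows. The wording is a clerical slip: a stage number that appears to come from the three-stage clamp, used for a clamp with two unnumbered steps. The document's own definition resolves it to 8 mU/m²/min, and an analyst working from the whole protocol would use that step.

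The scope is one secondary outcome, in a group that section IV.A labels as confirmatory and exploratory, in a pilot planned for 30 completers. The two primary outcomes, the sample size and the stated power do not depend on it. No sample is lost under either reading, and no effect on any result has been shown.

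The conclusion assumes that the outcome list uses the stage label in the sense defined in section III. The document does not say so outright, but it offers no other sense. Writing the insulin rate beside the outcome when results are reported would be good housekeeping and would not alter the analysis.

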- Weight instability (weight change >5% in last 6 months)
- History of any organ transplant, including islet cell transplant
- Current or prior infection with HIV, hepatitis B or hepatitis C, or transaminases >2x ULN
- Any condition, medical or otherwise that would, in the opinion of the investigator, prevent complete participation in the study, or that would pose a significant hazard to the subject
- History of substance abuse within the 12 months prior to screening

Screening: A phone screen will be followed by provision of the consent form and a screening/enrollment visit at the outpatient CTRC. This visit will include the consent process, history, physical exam, non-fasting screening labs [β -HCG, HbA1c, metabolic panel, TSH, urine microalbumin, and CBC], detailed menstrual history for women, and a DEXA scan for body composition and estimation of caloric needs.

Study design:

T1D subjects (n=30) will have a fixed order of treatment (placebo-metformin) and will be given their first medication after screening is complete and eligibility confirmed. Medications (metformin 500, 1000mg and identical placebo) will be dispensed by the pharmacy and the subject will be blinded to the fixed order of the medications to avoid biased treatment effects throughout the intervention period. As in previous Barbara Davis Center (BDC) metformin studies, this study will use the CTRC pharmacy to dispense the active drug and placebo. Both are provided by Caraco manufacturer. My colleagues at the BDC already purchased tooling for the Caraco brand placebo tablets and the company has agreed to make more placebo tablets for this study as necessary to cut out the upfront cost of tooling.

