Subjects will be instructed to take study drug at 500mg at bedtime for the first week, 500 mg twice daily for the second week, 500/1000mg daily for one week and 1000mg twice daily for the remainder of the 6 week period. Subjects who fail to tolerate an uptitration will be held at the prior dose for an additional 3 days and then retried. Subjects who have not reached at least 500 mg BID dosing by the end of week 3 will be withdrawn from the study. Thus, final metformin dosing will be 500 BID or 1000 BID. During the last three days of each treatment phase, subjects will be placed on a standardized typical diabetic diet (40% carbohydrate, 35% fat, 25% protein; based on CACTI food records) for three days prior to late evening admission on day 3 to the CTRC. Overnight admission is critical to ensure that all subjects are in the same state prior to each testing session. Remaining pills will be turned in to allow a pill count as a measure of compliance. Subjects will be transitioned to an insulin drip for overnight glucose control using the protocol previously used for CTRC protocol 1499 (see appendices for starting doses and titration schedule). Inpatient studies (baseline labs, vascular studies, biopsies, and hyperinsulinemic euglycemic clamp) will be performed the following day (Figure 4). After a two week to two month washout period, the full cycle will be repeated with the second intervention. Women will be tested at the same time in their menstrual cycle (day 4-9) after each intervention period. Allowing up to 2 months between interventions is necessary to allow this type of scheduling with the possibility of a missed cycle due to scheduling conflicts. The study timeline and detailed visit schedule are as follows:

Screening:

- Visit 1: Screening visit - consent process, H&P, non-fasting labs, DEXA, dietary questionnaire

Stage 1 (Study drug A, Placebo):

- Visit 2: Stage 1 start visit (day A1) – Insert CGM and receive instruction on use and download, pick up Placebo, Instructions from PI re med dosing and insulin dose self-adjustment
- Visit 3: Stage 1 CGM follow-up visit (day A8) – in person CGM download and reinsertion of sensor for the next week. Review glucoses with PI.
- Visit 4: Stage 1 prestudy day visit (day A39) – pick up three day diet and receive instructions on insulin dosing and times for the pre-study day. Accelerometer set-up
- Visit 5: Admission for Placebo study day (Days A42, 43) – see below

2 weeks- 2 months wash-out

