Subject discontinuation criteria: (1) Failure to tolerate uptitration to a dose of metformin of at least 500 mg BID within 4 weeks, (2) Patient report of increased hypoglycemia not resolved with insulin dose adjustments within 2 days, (3) Other events or adverse reactions that are possibly related to study drug, that are contraindications to study drug, or that interfere with study measures.

Protocol stopping rules: Occurrence of any severe adverse reaction including but not limited to hypoglycemia leading to unconsciousness or requiring external assistance will immediately be discussed with the data safety officer to evaluate need for protocol termination. Occurrence of more than one such event will lead to an immediate discontinuation of the protocol.

D. Description, Risks and Justification of Procedures and Data Collection Tools:

Methods: All measures will be assessed post 6 weeks of each of two blinded study drugs (metformin and placebo).

Continuous glucose monitoring: Subjects will have continuous glucose monitoring (CGM, (DexCom 7-plus® system)) through both intervention periods. This will be real-time during the first four weeks (insulin dose adjustment and increased safety) and blinded during the last two weeks (statistical adjustment for changes in glycemic control).

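### Placebo always precedes metformin, so the paired t-tests for GIR and FMD estimate drug plus any period effect; the limitations omit this, and no masking of the FMD reader is described

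*Combined protocol and SAP*

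**What the plan says.** Section IV.B (Overall research plan) sets out a "single-blinded, fixed-order, placebo-controlled cross-over design study in T1D subjects". The reason given for the fixed order is that metformin has lasting residual effects and the washout needed is unknown. Under Study design, "the subject will be blinded to the fixed order of the medications to avoid biased treatment effects"; no one else is said to be blinded. The visit schedule labels the two assessment admissions by treatment: "Visit 5: Admission for Placebo study day (Days A42, 43" and "Visit 8: Admission for Metformin study day (Days B42,43".

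Section IV.D (Methods) states: "All measures will be assessed post 6 weeks of each of two blinded study drugs (metformin and placebo". Section IV.F compares the post-period measures within participants by paired t-test. It adds a mixed model with continuous glucose monitoring (CGM) covariates for insulin sensitivity only.

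The FMD paragraph in IV.D gives the device, scan site, cuff procedure and analysis software. It does not say who reads the recordings or what the reader can see. For the 31P-MRS substudy, once ten participants have completed, "an interim analysis, including unblinding of these 10 subjects, will be performed".

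Section IV.E lists six limitations: sample size, treatment length, tracer use, surrogate outcomes, glycemic change, and other confounders such as activity, illness, hormones and stress. Order and period are not among them.

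**The concern.** In a single-sequence crossover, treatment and period change together. Anything that would have moved GIR or FMD between the two study days without metformin is counted as drug effect. Section IV.E reads a rise in GIR as support for metformin, and reads no change as a sign that insulin resistance and cardiovascular risk work differently in type 1 diabetes. Both readings need the assumption of no period effect, since drift could mimic a benefit or hide one. The assumption is never stated.

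The fixed order also bears on masking. A reader who knows the design and sees a visit date or stage label knows the treatment. FMD is a primary outcome read from recordings, so expectation at the reading stage is a possible further source of shift, and one that can be removed cheaply. The stakes go beyond this pilot, because IV.E expects a favorable result to support a longer study of clinical outcomes.

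**Working it through.** **1. What the paired test estimates.** Let D be the metformin-period value minus the placebo-period value for one participant, τ the drug effect and π the period effect. With placebo always first, E(D) = τ + π. A period term would be identical to the treatment term, so no model fitted to these data can separate the two. A larger sample narrows the interval around τ + π but does not remove π. The CGM mixed model adjusts insulin sensitivity for measured glycemia; it does not cover FMD or non-glycemic drift.

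**2. The plan's own power figures (IV.F).** Method: paired t-test, noncentral t, n = 30, 29 degrees of freedom. The plan states no alpha; two-sided 0.05 is assumed and reproduces its figures.
- Insulin sensitivity: difference 0.5, SD of the difference 1 (M/I units). Noncentrality = 0.5 × √30 = 2.74, power 75.4% (stated 75%).
- FMD: SD of the difference = √(2.1² + 1.9² − 2r × 2.1 × 1.9). At r = 0 this is 2.83. For 1.5 points, noncentrality = (1.5/2.83) × √30 = 2.90, power 80.1% (stated 80%).

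These are powers to detect τ + π. They are powers to detect the drug effect only if π = 0.

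**3. Illustration of sensitivity.** The shifts below are assumed; the documents supply none.

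| Case | Shift (SD of D) | Chance of p < 0.05 |
|---|---|---|
| No drug effect | 0 | 5% |
| No drug effect | 0.1 | 8.3% |
| No drug effect | 0.25 | 26.3% |
| True FMD effect 1.5 points, SD 2.83 (r = 0) | −0.25 | 31.6%, from 80.1% |
| True FMD effect 1.5 points, SD 2.01 (r = 0.5) | −0.25 | 74.9%, from 97.7% |

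In outcome units, 0.25 SD is 0.25 × 2.83 = 0.71 FMD points at r = 0, or 0.25 × 2.01 = 0.50 at r = 0.5. On the plan's M/I scale it is 0.25, half the planned difference of 0.5; that shift against a true effect of 0.5 would cut power from 75.4% to 26.3%.

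**4. Masking, passages side by side.** Study design blinds the participant. Methods calls the drugs blinded without saying to whom. The FMD paragraph is silent on the reader. The schedule names the study days by treatment. The substudy text speaks of unblinding but does not say who was masked until then. Taken together, no masking of the FMD reader is described, and the fixed order makes date or stage equivalent to treatment.

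**The case against.** The strongest reply is that this is a disclosed and sensible trade-off. Carryover is a good reason not to randomize the order, drug plus period is inherent in any single-sequence design, and a reader told the order is fixed can see it. The plan also limits drift: weight-stable participants, weekly glucose review with insulin adjustment, a standard diet, overnight admission, menstrual timing, stable activity, and rescheduling for illness. Section IV.E is cautious in places, since it says a smaller effect may be missed in so small a sample and that a larger, longer study would be needed. All of this stands. It reduces the weight of the point but does not answer it: the controls limit drift without measuring it, and the caveat on a null result concerns sample size, not period.

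On masking, the documents are silent rather than adverse. A reader might infer that the FMD reader is unmasked. They do not say so, and nothing shows that recordings carry the schedule's treatment labels.

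A reader might also infer a built-in drift from the week-1 visit, which is scheduled in stage 1 ("in person CGM download and reinsertion of sensor for the next week. Review glucoses with PI") and optional in stage 2 ("Option for one week visit 6b if desired for first repeat CGM insertion"). The documents do not support that. Weekly review by the investigator is planned throughout treatment, the stated purpose of the in-person visit is to check sensor reinsertion, and the preliminary data report no correlation of CGM measures with GIR.

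**Conclusion.** The point holds in a limited form. The paired analyses of GIR and FMD estimate drug plus any period effect, the limitations do not say so, and the interpretation of both a positive and a null result rests on an unstated assumption. Masking of the FMD reader is not described in a design where date reveals treatment. A change should be made, because the remedy is cheap and alters what the trial may conclude.

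Two stronger readings are not supported. One is that the fixed order is an error to be reversed; the carryover reason is sound. The other is that the trial's false-positive rate is 26%, or its FMD power 32%. Those figures follow from an assumed 0.25 SD shift, and the second also from zero within-participant correlation. The documents give no evidence of the size or direction of any drift, nor of any reader bias.

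**What to change.** Keep the order, and make two changes.

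1. **FMD reading.** Existing staff other than the reader remove date, visit and stage labels from the stored recordings and assign random codes. The existing reader analyzes each participant's two recordings in random order before codes are released. At the 31P-MRS interim unblinding, FMD codes stay sealed for any pair not yet read.
2. **Limitations and analysis plan.** Add period confounding to the limitations in IV.E. Report GIR and FMD as metformin-period minus placebo-period differences with 95% confidence intervals. Attribute a difference to metformin, or read a null result as IV.E does, only under a stated assumption of no period effect.

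The cost is relabelling work, later FMD results (each pair waits for stage 2) and some rewording. No visit or procedure is added. The documents do not say who acquires and who reads the FMD images; if one person does both, someone else must do the recoding and the masking is only partial. Period confounding itself remains, as does any bias in clamp conduct or image acquisition.
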